#### **AIM3:**

We will use a chi-square test to compare lung screening rates between patients receiving care at CHCs to patients from other practices within the MGH primary care network during the one-year study period.

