## **I. SPECIFIC AIMS**

**Specific Aim 1:** To develop a patient navigator (PN) program for lung screening for patients who are current smokers, aged 55-77 years, potentially eligible for lung screening and are receiving care at community health centers (CHCs) affiliated with MGH.

**Specific Aim 2:** To evaluate the effectiveness of the new lung screening PN program in improving screening rates and increasing use of tobacco cessation services in a randomized controlled trial.

**Specific Aim 3:** To demonstrate that equity is maintained in rates of lung screening and in follow up of abnormal chest CT results, comparing eligible smokers from CHCs with eligible smokers from other practices within the MGH primary care network.

**Specific Aim 4:** To collect quantitative data about patient satisfaction with the navigators in the lung screening PN program

**Specific Aim 5:** To explore CHC primary care providers opinions about the lung screening PN program via survey

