#### **V.4. Randomized Clinical Trial (Specific Aim 2)**

To test our hypothesis we will randomize eligible patients receiving care at CHCs to one of two study groups:

Early intervention	Usual care/delayed intervention
400 patients will receive 1:1 PN to obtain lung screening and follow-up of abnormal results, as well as smoking cessation guidance	800 patients will receive usual care during the 1-year study period. After the study period they will be offered 1:1 PN to obtain lung screening and follow-up of abnormal results as well as smoking cessation guidance

Eligibility criteria:

1. Inclusion criteria: adult patients aged 55-77 years who are current cigarette smokers (according to an algorithm using EMR data), and receive care at one of the five MGH CHCs.
2. Exclusion criteria: 1) patients who have previously received a diagnosis of lung cancer per EMR, 2) have undergone a chest CT within 18 months before enrollment, 3) are subsequently identified as having died prior to the study intervention 4) deemed by their primary care provider as not eligible for lung screening

Patients will be identified using existing electronic systems developed by the MGH Primary Care Operations Improvement (PCOI) program (Protocol # 2004P002796).

Using a newly developed TopCare smoking and lung screening registry, we will identify smokers receiving care at MGH health centers who could be eligible for lung screening. We will e-mail primary care providers a list of their patients and ask them to notify us in a week if they do not want us to contact a patient and to provide a reason why they believe patient is not eligible for lung screening. The eligible patients will then be randomly allocated to the intervention or usual care groups. Patients randomly assigned to the intervention group will be eligible for PN, while patients randomly assigned to the control will receive usual care and be eligible for navigation after the one year period.

Patient navigator intervention:

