#### **V.5. Prospective Data Collection for Disparities in LDCT and Smoking Cessation (Specific Aim 3)**

To determine whether the patient navigator program maintained equity in obtaining lung screening among smokers from CHCs compared to smokers from other MGH primary care practices, we will examine lung screening rates in the two study populations in the year prior to the intervention and after the 1-year intervention period. Eligibility criteria are the same as in Specific Aim 2, except the analysis will include patients in all MGH affiliated primary care practices stratified by CHC or other.

Lung screening rates prior to and after the 1-year intervention period will be compared among eligible patients receiving care at one of the five MGH CHCs (all patients and subgroup of those who received the early intervention) and eligible patients from all other MGH practices.

Patients will be identified using existing electronic systems developed by the MGH PCOI program (Protocol # 2004P002796).).

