### Outcome measure

Percentage of current smokers aged 55-77 years at baseline who have a chest CT in the subsequent 1 year, comparing patients receiving care at CHCs with patients from all other practices within the MGH primary care network.

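### Aim 3 sets out to demonstrate equity, but its only named analysis is a study-year test for a difference, and the prior-year, subgroup and follow-up comparisons are not carried into the analysis plan

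*Combined protocol and SAP*

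**What the plan says.** Section I states the aim as "To demonstrate that equity is maintained in rates of lung screening and in follow up of abnormal chest CT results", comparing CHC smokers with smokers from the rest of the primary care network.

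Section V.5 describes the design. On timing: "we will examine lung screening rates in the two study populations in the year prior to the intervention and after the 1-year intervention period". The CHC side is taken in two ways: "all patients and subgroup of those who received the early intervention". On the population: "Eligibility criteria are the same as in Specific Aim 2", widened to all affiliated practices. In V.4 those criteria exclude patients who "have undergone a chest CT within 18 months before enrollment" and patients "deemed by their primary care provider as not eligible for lung screening". Section IV gives the CT look-back as the last year instead.

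The Aim 3 outcome measure in VI.2 is narrower: "Percentage of current smokers aged 55-77 years at baseline who have a chest CT in the subsequent 1 year", CHCs against all other practices. The AIM3 paragraph of VI.3 is narrower still: "We will use a chi-square test to compare lung screening rates between patients receiving care at CHCs to patients from other practices", limited to the one-year study period. Section VI.4 sizes Aim 2 only. The only confidence intervals in the plan are for the Aim 2 process measures.

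**The concern.** A chi-square test asks whether two rates differ. Failing to reject does not establish that they are alike, at any sample size. It also does not say how large a CHC deficit has been excluded. As written, the plan has no result that could count as a demonstration of equity, and a null result invites being read as one.

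The word *maintained* implies a comparison with an earlier period. Section V.5 plans one, but neither the outcome measure nor the analysis carries it. If it were run on the early-intervention patients under the stated eligibility, their rate would start at about zero because of how they were selected, and the rise would be an artefact.

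The second half of the aim, equity in follow-up of abnormal CTs, has no analysis between CHCs and other practices.

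**Working it through.** **1. The Aim 3 passages side by side**

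| Element | Section I | V.5 | VI.2 outcome | VI.3 AIM3 |
|---|---|---|---|---|
| Study-year CT rate, all CHC patients vs other practices | yes | yes | yes | chi-square |
| Prior-year rate | implied by *maintained* | yes | no | no |
| Early-intervention subgroup vs other practices | no | yes | no | no |
| Follow-up of abnormal CTs, CHC vs other | yes | no | no | no |
| CI, margin or decision rule | no | no | no | no |

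Timely follow-up is defined in VI.2 item 3 (recommended interval plus 30 days; 60 days for biopsy or PET), but VI.2 and VI.3 compare it only between trial arms. What is missing is the contrast between settings, not the definition.

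**2. How often a real deficit would pass as non-significant**

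The plan gives no Aim 3 figure to reproduce; its 88% power belongs to Aim 2. Inputs:
- CHC patients: about 1200 (Section III).
- Patients in other practices: not given; assumed 1200 to 5000.
- Rates: not given for either setting. Section III offers an anchor: 204/1480 = 13.8% had a chest CT in 18 months and/or lung cancer (2012 data, ages 55-79). Scaled, 13.8% × 12/18 = 9.2%; under a constant hazard, 1 − (1 − 0.138)^(2/3) = 9.4%. So roughly 9% a year.

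P(non-significant) = Φ((1.96·s0 − d)/s1), where d is the true deficit, s0 the pooled and s1 the unpooled standard error; the opposite tail is negligible. For 9% vs 12% with 1200 per group, s0 = 0.01251 and s1 = 0.01250. This gives (0.02452 − 0.03)/0.01250 = −0.438, and Φ = 0.331.

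| True rates (CHC vs other) | Others = 1200 | 2400 | 5000 |
|---|---|---|---|
| 9% vs 12% | 0.331 | 0.216 | 0.146 |
| 10% vs 12% | 0.653 | 0.571 | 0.508 |
| 7% vs 9% | 0.561 | 0.464 | 0.391 |

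**3. What a confidence interval would show**

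Half-width at a 10% rate = 1.96·√(0.09·(1/1200 + 1/n)): 2.4 points for n = 1200 and 1.9 points for n = 5000. This is the information the test alone leaves out.

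**4. The prior-year rate in the early-intervention subgroup**

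These patients had to be free of a chest CT for 18 months before enrollment (V.4) or for the last year (Section IV). Either look-back covers the prior year, so their prior-year rate is about 0% before any data are seen.

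**5. What the all-CHC contrast can say about navigation**

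Only 400 CHC patients are navigated in the study year; the rest receive usual care. A 5-point navigator effect (VI.4) moves the all-CHC rate by 400/1200 × 5 = 1.7 points, or 400/1276 × 5 = 1.6 points with the total in VI.4.

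**The case against.** The strongest reply is that V.1 lists this comparison among the secondary outcomes, that it is not randomised, and that the chi-square may be meant descriptively. The standing of the comparison is as stated, and it limits the seriousness. But equity is a numbered aim whose verb is *demonstrate*, and Section II gives the prevention of disparities as part of the rationale. It is also fair that a formal margin is not the only repair: rewording the aim as a comparison is equally sound, and the chi-square need not be removed.

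Four stronger readings are tempting but not supported:

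- A reader might infer that the prior-year rate is zero for everyone. That holds only if one cohort is fixed at enrollment. Applying the VI.2 baseline definition at the start of each year avoids it for the full cohorts.
- A reader might infer that ignoring clustering by practice invalidates the test, or that it can produce only false differences. VI.2 compares the five CHCs with all the other network practices, and no passage claims wider inference, so this is a point to clarify. If wider inference were intended, clustering could hide a true deficit as well as create a false one, depending on power.
- A reader might take 9.2% a year as an upper limit. It is not: repeat scans would raise the annual figure, while counting lung cancer diagnoses pushes the other way.
- A reader might extend the criticism to the randomised comparison. The Aim 2 primary analysis does not depend on any of this.

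**Conclusion.** The concern holds and should be fixed. Followed as written, Aim 3 cannot support its stated conclusion, and this does not depend on any assumed number. The illustrative sizes do: with 1200 to 5000 patients assumed in other practices and the assumed rates above, a 3-point deficit (9% vs 12%) is missed 33% to 15% of the time and a 2-point deficit (10% vs 12%) 65% to 51%.

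The mismatches between Section I, V.5, VI.2 and VI.3 are plain on the text. So is the near-zero prior-year rate in the early-intervention subgroup. Two further limits belong with the conclusion. Provider review is part of Aim 2 eligibility but is described only for health-center patients, so the two settings may be filtered differently. And the all-CHC contrast describes a mixed population, about two thirds of it not navigated, so neither equity nor inequity there can be credited to the navigator program alone.

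**What to change.** Amend V.5, the Aim 3 outcome measure in VI.2 and the AIM3 paragraph of VI.3, with Section I where noted.

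- **(a) Main contrast.** Report the study-year chest CT rate in all CHC patients minus that in all other practices, with its 95% CI, using the same EMR-based criteria everywhere. The chi-square may stay. Either claim equity only if the lower limit lies above a margin that the sponsor pre-specifies and justifies, or reword Section I as a comparison and make no equity claim. State that the contrast describes a mixed CHC population and not the navigator program.
- **(b) Prior year.** Either delete it and reword *maintained* in Section I, or add it to VI.2 and VI.3 with a separate cohort indexed at the start of each year and one CT look-back, reconciling Section IV with V.4. Keep it only if past smoking status and earlier CTs can be rebuilt; Section IV describes the registry as holding the most recent chest CT.
- **(c) Early-intervention subgroup.** Make no before-after comparison. Report its study-year rate against other practices with a CI, noting the provider screening.
- **(d) Scope.** State in one sentence whether inference is for these named practices only; if not, allow for clustering by practice in the CI.
- **(e) Follow-up of abnormal CTs.** Either apply the timely follow-up definition in VI.2 item 3 to CHCs versus other practices with a CI, or limit the Aim 3 conclusion to screening rates.

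Cost: items (a), (c) and (d) need wording and a sponsor decision on the margin, with no data beyond what Aim 3 already requires. Keeping the prior year needs a further extract that the documents do not show to be feasible. Keeping the follow-up comparison extends chart review to the other practices. The downside is that the study may end with no equity claim.

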### **III. SUBJECT SELECTION**

According to internal MGH data from 2012, 1480 patients aged 55-79 years at MGH CHCs were current smokers. Of these patients, 204 had a chest CT scan in the prior 18-months and/or had a diagnosis of lung cancer. Because of new Medicare guidelines we will only include patients that are aged 55-77 years and additionally exclude patients that providers deem ineligible for lung cancer screening. We estimate the total number of patients eligible for our interventions to be around 1200. Our experience in prior PN colorectal cancer screening interventions is that one full-time navigator assigned 400 patients will be able to reach/work with 300 patients over a 9-month period. Since our navigator will also follow-up abnormal CT results, our study will last one year. Eligible patients will be identified, randomized, and an electronic list of patients will be downloaded into an existing TopCare navigator data base. The navigators will use this system to track patients and interventions. Patients randomized to the interventions group will be recruited by navigators during their visits to the health center or over the phone. Since the navigator program is already standard of care at MGH, its expansion to include lung screening is considered part of usual care.

For Specific Aim 5, primary care physicians (PCPs) and nurse practitioners (NPs) from the community health centers with the PN program will be asked to complete a survey following the study period. There are approximately 81 PCPs and NPs who will be asked to complete the survey.

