## **V. STUDY PROCEDURE**

### **V.1. Overview**

We propose to develop, implement, and rigorously evaluate a novel lung screening patient navigator program for patients that currently smoke in five community health centers affiliated with a primary care network of a large academic hospital.

Eligible patients will include those receiving care in community health centers who are 55-77 years old and currently smoking. The intervention trial will be randomized at the patient level. In the intervention group, patients will be contacted by a culturally competent PN who will help them stop smoking and obtain lung screening. The control patients will receive usual care. The primary outcome will assess the percentage of eligible patients in intervention and control groups who had at least one chest CT during the study period. Secondary outcomes will include as-treated primary outcomes among intervention patients contacted by the patient navigator, primary outcomes stratified by language spoken, race, age, and practice site, follow-up of abnormal results, percentage of patients with tobacco treatment, and comparison of lung screening to other practices in the primary care network.

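### Aim 3's chi-square ignores clustering by practice, so its error rate exceeds 5%, by an amount the documents do not fix, if the result is read beyond these practices

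*Combined protocol and SAP*

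**What the plan says.** Section VI.3, AIM3, consists of one sentence: "We will use a chi-square test to compare lung screening rates between patients receiving care at CHCs" with those at the network's other practices during the study year. It names no practice term, clustered variance, interval or margin.

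The outcome measure for Aim 3 in section VI is the percentage of baseline current smokers with a chest CT in the following year, "comparing patients receiving care at CHCs with patients from all other practices within the MGH primary care network". Section V.5 adds that "the analysis will include patients in all MGH affiliated primary care practices stratified by CHC or other". Eligibility otherwise follows Aim 2, so the CHC side is the population that "receive care at one of the five MGH CHCs" (section V.4).

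The purpose, in section I, is "To demonstrate that equity is maintained in rates of lung screening and in follow up of abnormal chest CT results".

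Practice characteristics appear in the analysis plan only as predictors in the Aim 2 logistic models and as an Aim 2 subgroup factor. Section V.5 also plans to compare rates before and after the intervention year, but VI.3 gives no method for that.

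**The concern.** In Aim 2 patients are randomised individually, so each arm is represented within every practice and differences between practices largely cancel. In Aim 3 the compared factor never varies within a practice. If practices differ in how readily they order chest CT, for reasons unrelated to being a CHC, that difference goes straight into the CHC-versus-other contrast. A patient-level chi-square has no term for it.

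The plan itself expects such differences. It stratifies the Aim 2 outcome by practice site and lists provider and practice characteristics as predictors of screening. The route to screening also runs through providers: section II describes a written order and a shared decision visit, and section V.4 lets the primary care provider rule a patient ineligible.

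At stake is a reported CHC disparity, or advantage, that reflects ordinary variation among a few practices, with an interval that looks more precise than it is.

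**Working it through.** **The plan's own figure.** No power, margin or error rate is given for Aim 3. The only computed figure, 88% power in VI.4, belongs to the randomised Aim 2 comparison (400 v 1276 − 400 = 876, 5-point difference). The control rate is not stated. At an assumed 5% v 10%, two-sided power is 89.2%, or 87.1% with continuity correction, so the figure is plausible. It has no bearing on Aim 3.

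**Inputs from the documents.** There are five CHCs. Section III says "We estimate the total number of patients eligible for our interventions to be around 1200", and VI.4 uses 1276. That is 1200/5 = 240 to 1276/5 ≈ 255 patients per CHC if they are of equal size. Alpha is 0.05 in VI.4; none is stated separately for Aim 3.

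**Assumptions, because the documents are silent.** 10 to 30 other practices of 50 to 250 eligible patients each; ICC 0.001 to 0.02; two-sided test; practices viewed as a sample from a wider set.

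**Step 1, CHC side alone.** Design effect = 1 + (240 − 1) × ICC. This is 1.5 at ICC 0.002, 2.2 at 0.005, 3.4 at 0.01 and 5.8 at 0.02. The between-practice part outweighs the binomial part only when 239 × ICC > 1, that is, ICC above about 0.004.

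**Step 2, the contrast.** With N₁, N₂ patients and m₁, m₂ patients per practice on the two sides, the ratio of clustered to independent variance of the difference is

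D = 1 + ICC × [(m₁ − 1)/N₁ + (m₂ − 1)/N₂] / [1/N₁ + 1/N₂],

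and the true error of a nominal 5% test is 2 × [1 − Φ(1.96/√D)].

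Example: five CHCs (N₁ = 1276, m₁ ≈ 255) against 10 practices of 250 (N₂ = 2500). The bracket ratio is about 252, so at ICC 0.01, D = 3.52, 1.96/√3.52 = 1.04, and the error is 29.6%. Against 30 practices of 50 (N₂ = 1500) the ratio is about 160, D = 2.60 and the error is 22.4%. These two layouts bracket the others tried:

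| ICC | D | True error of the 5% test |
|---|---|---|
| 0.001 | 1.16-1.25 | 7-8% |
| 0.002 | 1.32-1.51 | 9-11% |
| 0.005 | 1.80-2.26 | 14-19% |
| 0.01 | 2.60-3.53 | 22-30% |
| 0.02 | 4.20-6.06 | 34-43% |

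For scale, at a 10% CT rate an ICC of 0.01 is a between-practice SD of √(0.01 × 0.10 × 0.90) = 3 percentage points.

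**Step 3, simulation.** Beta-binomial data with no true difference (20,000 replicates; CT rates 5%, 10% and 20%; 10 or 15 other practices) gave chi-square error of 9-11%, 15-19%, 22-30% and 34-43% at ICC 0.002, 0.005, 0.01 and 0.02. A t-test on practice-level rates had about 3-5% error throughout.

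**Step 4, practices held fixed.** Treating the practices as a fixed, complete set (40,000 replicates) gave chi-square error of 4.5-4.9%: no inflation.

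**Step 5, interval width.** At a 10% rate, ICC 0.01 and 15 other practices of 150, the independent SE is √[0.09 × (1/1276 + 1/2250)] = 1.05 points, half-width 1.96 × 1.05 ≈ 2.1 points. The clustered SE is √[0.09 × (3.54/1276 + 2.49/2250)] = 1.87 points. With t on 5 + 15 − 2 = 18 df (2.10), the half-width is about 3.9 points.

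**The case against.** The strongest reply is that Aim 3 concerns one network and includes all of its practices. If the question is only whether CHC smokers in this network had chest CT at the same rate as the others in that year, differences among practices are part of the answer, and Step 4 shows that the chi-square then holds its level. This stands, and it limits the point. But no section confines Aim 3 to that description. The stated purpose is to show that equity is maintained under a navigator program, which invites a reading about CHC status itself. If the descriptive reading is intended, the plan should say so.

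A reader might infer that the error rate is simply far above 5%. The documents do not support that as a fact: they give no ICC and no number or size of other practices, and at ICC 0.001 the error is only 7-8%. Nor can one say that the test would report a false disparity. Even at ICC 0.01, 70-78% of null datasets would show no significant difference.

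The before/after comparison in section V.5 could remove stable practice differences. That is fair, but VI.3 specifies no such analysis, and the only stated test uses study-year rates.

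Finally, a test that rejects too often works against a claim of equity, not for it. That is correct. The lack of an equivalence margin is a separate gap, and a wider interval does not fill it.

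**Conclusion.** The point holds conditionally. The only stated Aim 3 test treats patients as independent on a factor that is fixed by practice, with five practices on one side, and nothing elsewhere in the plan repairs this. For any inference beyond these practices in this year, its error exceeds 5% and its interval is too narrow.

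The direction follows from any positive ICC. The size rests on the assumed ICC and on the assumed number and size of the other practices: modest at ICC 0.001, roughly three to four times nominal at 0.005, and larger above that. For a purely descriptive comparison of this network there is no inflation. The randomised Aim 2 comparison is not affected.

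**What to change.** In VI.3, AIM3, replace the chi-square with the difference in patient-level CT percentages and a 95% CI that accounts for clustering by practice. Two routes would serve:

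- a mixed or GEE model with practice as the cluster and a small-sample correction, with the result expressed as a difference in percentages; or
- a practice-level t interval weighted by practice size. Without weights it would estimate the mean practice rate instead of the percentage of patients that the Aim 3 outcome measure defines.

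Show the practice-specific rates alongside. If the chi-square is kept, state that its result describes only these practices in this year.

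The cost is plan wording, a small amount of analysis and a wider interval. No new data are needed, since practice membership already determines who is a CHC patient. The change does not provide an equity margin: a non-significant result would still not demonstrate equity, and a wider interval must not be read as making that case.
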